9.1.10 Fundus Exam

A dilated funduscopic exam will be performed to evaluate the vitreous, retina, choroid and optic nerve. Fundus findings will be noted, described and graded as normal or abnormal. Qualitative descriptions will be provided for any abnormal findings. A fundus examination will be completed at **Screening**, **Day 4**, **Week 1**, **Week 2**, **Week 3** and **Week 4**.

9.1.11 Corneal Pachymetry

Central corneal thickness will be measured by applanation ultrasound pachymetry. For each measurement the highest and lowest of five consecutive readings will be discarded, and the average of the remaining three will be recorded. In cases where a pachymeter is used that

calculates an average central corneal thickness from five or more measurements with a single touch to the eye, this average measurement may be used for the purposes of calculating the pachymetry corrected IOP. Corneal pachymetry will be completed at **Screening**.

9.1.12 Dosing Instructions

All subjects will receive written dosing instructions about how to properly administer their eye drops along with a printed dosing diary in which to document each dose. At Visit 1, the staff will review these materials with the subject and confirm that the subject understands the instructions on how to dose and how to complete the diary. Subjects will be instructed to bring the dosing diary with them to Visit 3 through Visit 6 to be reviewed by the site staff. The site staff will ensure compliance and review/ remind the subject on instructions as needed.

Missed Doses: If subjects forget to take a dose at the scheduled time, they should take that dose as soon as they remember and record the time of dosing in the dosing diary.

Exceptions: Subjects should not take a "make-up" dose within one hour of another scheduled dose. Instead they should take the next scheduled dose and note the missed dose on the dosing diary.

9.2 Adverse Events and Serious Adverse Events

9.2.1 Adverse Events

Adverse Event

An AE is any untoward medical occurrence in a patient or clinical investigation patient administered a study drug, which does not necessarily have a causal relationship with this treatment. An AE can therefore be any unfavorable and unintended sign (including an abnormal laboratory finding), symptom, or disease temporally associated with the use of the study drug whether or not it is considered related to the study drug. AEs will be collected from the time the subject signs the informed consent form through 30 days after the last study drug administration.

Abnormal laboratory and other abnormal investigational findings (i.e., physical exam) should not be reported as AEs unless they are associated with clinical signs and symptoms, lead to treatment discontinuation or are otherwise considered clinically relevant by the investigator. In cases of surgical or diagnostic procedures, the condition/illness leading to such a procedure is considered as the AE rather than the procedure itself. In case of a fatality, the cause of death is considered as the AE, and the death is considered as its outcome.

Events Not to Be Considered as Adverse Events

Pre-existing medical conditions/signs/symptoms present before the screening period that do not worsen in severity or frequency during the study are defined as baseline medical conditions, and are not to be considered AEs.

All AEs must be recorded in the site's study records and the AE CRF with the following information:

1. Relationship to Study Drug: The Investigator must assess whether they consider an AE to be drug-related. In assessing this relationship, the Investigator must use information about the drug as outlined in the Investigator's Brochure (IB), the subject's pre-existent medical conditions/concurrent medication, and chronology of the event relative to drug administration.

The following definitions will be used:

- **Definitely or possibly related** applies to those AEs that, after careful medical consideration at the time they are evaluated, are considered by the Investigator (or other qualified physician) to have at least a possible relationship to study drug.
- Unlikely or not related applies to those AEs that, after careful medical consideration at the time they are evaluated, are considered by the Investigator (or other qualified physician) to have no relationship, or an unlikely possibility of a relationship, to study drug.
- 2. Event Severity: The Investigator will be asked to use their medical judgment to assess the severity of the AE.

The following are guidelines to be used by the Investigator to judge the event severity of an AE:

- 3. Duration: Start and end dates and times, or if continuing.
- 4. Frequency: whether the event is a single episode, recurrent or continuous.
- 5. Action taken.
- 6. Whether it constitutes a SAE, per definition below.
- 7. Outcome: resolved, resolved/ with sequelae, continuing, death, or unknown (only for subjects that are lost to follow-up).

The Investigator (or designee) should attempt to establish a diagnosis of the AE based on signs, symptoms and/or other clinical information. In such cases, the diagnosis, and not the individual signs/symptoms or laboratory abnormalities, should be documented in the subject's source documentation and the CRF unless the etiology of the event is unknown. An assessment should be made at each visit (or more frequently if necessary) of any changes in severity, the suspected relationship to study drug, the interventions required to treat it and the outcome.

9.2.2 Treatment Emergent Adverse Events (TEAE)

A TEAE will be an AE that occurred during the study after the first dose of study drug or that was present prior to dosing and exacerbates after the first dose of study drug.

9.2.3 Serious Adverse Events

An SAE is any AE that results in any of the following outcomes:

- Death: This includes death unrelated to the study drug (e.g. car accident). If a subject dies during the study and an autopsy is performed, autopsy results will become part of the subject's study chart and a copy should be sent to the Sponsor.
- Life-threatening experience. Life-threatening means that the patient was at immediate risk of death from the reaction as it occurred (i.e., it does not include a reaction which hypothetically might have caused death had it occurred in a more severe form).
- Required or prolonged inpatient hospitalization: Exceptions will be hospitalizations for a) elective or preplanned treatment for a pre-existing condition that is unrelated to the indication under study and has not worsened since the start of study drug or b) treatment on an emergency outpatient basis for an event not fulfilling any of the definitions of a SAE and not resulting in hospital admission
- Persistent or significant disability/incapacity
- Congenital anomaly
- Important medical events that may not result in death, be immediately life threatening, or require hospitalization may be considered a SAE when, based upon medical judgment,

they may jeopardize the patient and may require intervention to prevent one of the outcomes listed above.

9.2.4 Unexpected Adverse Event

An unexpected adverse event is defined as an AE, the nature or severity of which is not consistent with the information in the Investigator's Brochure for ADX-102.

9.3 **Reporting Serious Adverse Events**

The Investigator is responsible for reporting all SAEs, **regardless of causality**, to the Sponsor or their designated representative by phone or fax (or email) within 24 hours of learning of the occurrence. The reporting timeframe starts when the subject signs the informed consent form through 30 days after the last study drug administration. At a minimum, a description of the event and the Investigator's judgment of causality must be provided at the time of the initial report. These preliminary reports will be followed by detailed descriptions that will include copies of hospital case reports, autopsy reports, and other documents when requested and applicable.

Complications or progression of an initial SAE must be reported as a follow-up SAE Report to the original SAE, regardless of when the follow-up information is received by the Investigator. A follow-up SAE Report must be submitted within 24 hours of the Investigator receiving the follow up information. An SAE that is considered completely unrelated to a previously reported one should be reported separately as a new SAE.

In the event of a SAE, the investigator must immediately notify the **appropriate contact in the Study Manual**.

The procedures for reporting SAEs are as follows:

- Complete the "Serious Adverse Event Report Form". The Investigator may contact Pharmacovigilance via the telephone hotline for assistance with SAE reporting.
- Fax or email the SAE Form to the attention of Pharmacovigilance within 24 hours of the Investigator's knowledge of the event.

The original copy of the SAE Report Form and the fax confirmation sheet (or email) must be kept with the source documentation at the study site.

Follow-up information should be communicated the same way, using a new SAE Report Form stating that it is a follow-up to the previously reported SAE and giving the date of the original report. The follow-up information should describe whether the event has resolved or continues, if and how it was treated, and whether the subject continued or withdrew from study participation.

If the SAE was not previously documented in the Investigator's Brochure and is thought to be related to study drug, the Sponsor or their designee may urgently require further information from the Investigator for regulatory authority reporting. The Sponsor may need to issue an Investigator Notification to inform all investigators involved in any study with the same drug that this SAE has been reported.

The Investigator and study personnel should institute any supplemental investigations of SAEs based on their clinical judgment of likely causative factors. This may include clinical laboratory tests not specified in the protocol, histopathologic examinations, or consultations with specialists. The Sponsor or their designee may also request the Investigator to conduct supplemental assessments.

The Investigator should notify Pharmacovigilance of any SAE occurring after a subject has withdrawn from the study when such a SAE occurs within 30 days of the last dose of study drug and may reasonably be related to the study drug.

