6.4 Subject Withdrawal Criteria

Subjects may voluntarily withdraw from the study, or be removed from the study at the discretion of the Investigator or Sponsor, at any time. The Investigator may withdraw a subject

at any time if it is determined that continuing in the study would result in a significant safety risk to the subject.

If such withdrawal occurs, or if the subject fails to return for visits, the Investigator should determine the primary reason for a subject's premature withdrawal from the study and record the reason in the subject's study records.

Premature withdrawal may occur for any of the following reasons:

- Rescue therapy
- Non-compliance with the protocol requirements
- Death
- Adverse event (AE)
- Subject request
- Investigator request
- Sponsor request

For subjects who are lost to follow-up (i.e., those subjects whose status is unclear because they fail to appear for study visits without stating an intention to withdraw), the Investigator should show "due diligence" by documenting in the source documents all steps taken to contact the subject, e.g., dates of telephone calls, registered letters, etc.

All subjects prematurely discontinuing from the trial (prior to **Visit 6**), regardless of cause, should be seen as soon as possible for **Visit 6/EOT/ET** assessments (Section 5.4.4).

Subjects who are withdrawn from the study for any reason will not be replaced.

7 Treatment of Subjects

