7.3 Concomitant Medications

All medications that are taken by the subject in the 30 days prior to consent must be recorded during the **Screening (Visit 1)**. Any changes in dosage or new medications added as a result of intercurrent illness must be recorded in the CRFs.

Once it is determined that rescue therapy is needed the subject should be considered an Early Termination and the Week 4 (Visit 6) assessments should be completed.

7.4 **Prohibited Medications**

Use of the following medications is prohibited for the duration of a subject's participation in the study from **Screening (Visit 1)** through **Week 4 (Visit 6/EOT/ET)**:

- Any investigational treatment other than ADX-102
- Any medication part of exclusion criteria (See Section 6.2)

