10.5 Analysis Populations

The statistical analysis will be based on the analysis populations as defined below

Safety population	The safety population consists of all randomized subjects who receive at least one dose of study drug, regardless of whether or not they undergo any study assessments. Subjects in this population will be analyzed according to the treatment which they received. All safety analyses will be based on this population
ITT population	The intent-to-treat population (ITT) is the population of all subjects who are randomized into a treatment group. Subjects in this population will be analyzed according to the treatment group to which they were randomized. This population will be used for analyses of efficacy and pre-study/baseline characteristics.
PP population	The per protocol (PP) population is the subset of ITT subjects who meet all inclusion and exclusion criteria, remain on study medication, comply with treatment instructions, and do not have any significant protocol deviations or violations. Rescued subjects will not be excluded from PP solely on the basis of having been rescued and withdrawal of study medication and withdrawal from the study. Significant protocol violations prior to being rescued may exclude a rescued subject from the PP. Subjects in this population will be analyzed according to the treatment they receive.

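### Protocol 9.3 sets two causality rules for SAEs in the same 30 days after the last dose: all SAEs in general, but possibly related ones in subjects who have withdrawn, including rescued subjects

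*Protocol*

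**What the plan says.** Protocol 9.3 contains both rules. Its first paragraph states "The Investigator is responsible for reporting all SAEs, regardless of causality", and fixes the period: "The reporting timeframe starts when the subject signs the informed consent form through 30 days after the last study drug administration". That period is tied to dosing, and no exception is made for subjects who have left the study. The last paragraph of 9.3 turns to SAEs that arise after withdrawal and asks the investigator to notify Pharmacovigilance "when such a SAE occurs within 30 days of the last dose of study drug and may reasonably be related to the study drug".

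Rescued subjects belong to the withdrawn group. Protocol 6.4 introduces its list with "Premature withdrawal may occur for any of the following reasons", and rescue therapy is the first item. Protocol 7.3 says "Once it is determined that rescue therapy is needed the subject should be considered an Early Termination". The per-protocol definition in Protocol 10.5 says rescued subjects are not excluded "solely on the basis of having been rescued and withdrawal of study medication and withdrawal from the study", so it treats rescue as leaving the study.

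Elsewhere the 30-day window carries no causality condition. Protocol 9.2.1 says "AEs will be collected from the time the subject signs the informed consent form through 30 days after the last study drug administration", and the reminder given at the Visit 7 telephone call (Protocol 5.4.5) covers new AEs and SAEs over the same period without asking about relatedness.

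**The concern.** One section gives two answers to one question: must a site notify the sponsor of an SAE that it considers unrelated, if it occurs after withdrawal but within 30 days of the last dose? The first paragraph says yes. The last paragraph, read as the specific rule for withdrawn subjects, implies that notification is not being asked for.

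Two things are at stake. First, relatedness is a judgement that each site makes under masking. Pharmacovigilance needs to see a serious event before relatedness is settled, so this judgement should not decide whether the event is notified. Second, the condition is triggered by withdrawal, and rescue is a route to withdrawal. Time to rescue is itself a secondary endpoint compared between arms (SAP 9.2.4). A reporting rule that changes with an outcome of the trial is undesirable even when the numbers are small.

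**Working it through.** The plan gives no figure to reproduce here. The check is a comparison of texts, followed by an illustration of size on stated assumptions.

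**Step 1: the rules side by side**

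| Place | Who | Window | Causality condition |
|---|---|---|---|
| Protocol 9.3, first paragraph | all subjects | consent to 30 days from last dose | none; all SAEs |
| Protocol 9.3, last paragraph | withdrawn subjects | 30 days from last dose | reasonably related |
| Protocol 9.2.1 (AE collection, AE case report form) | all subjects | consent to 30 days from last dose | none; seriousness is a recorded item |
| Protocol 5.4.5 (Visit 7 reminder) | subjects reached by telephone | 30 days from last dose | none |

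Three of the four rows agree. Only the last paragraph of 9.3 differs, and it differs in the causality condition alone.

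**Step 2: what each row controls**

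The two paragraphs of 9.3 govern expedited notification to the sponsor. Protocol 9.2.1 governs what is recorded on the case report form, including whether the event is serious. A site that follows the narrow reading of 9.3 but complies with 9.2.1 still records the unrelated SAE. What is lost is the 24-hour notification.

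**Step 3: how long the ambiguity lasts**

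The window ends at the day of last dose plus 30. SAP 2.3.4.3 places rescue after the Week 1 or Week 2 assessments or later.

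- Last dose on Day 8: 8 + 30 = Day 38.
- Last dose on Day 15: 15 + 30 = Day 45.
- Last dose on Day 28 (completer): 28 + 30 = Day 58.

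The End of Study call is nominally on Day 36 ± 3. For a Day 8 or Day 15 last dose, a call on Day 36 leaves 2 or 9 days of the window afterwards.

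**Step 4: size, on assumptions**

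The documents give neither a rescue rate nor an SAE rate. Inputs:

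- n = 60 per arm, from about 120 subjects randomized 1:1.
- r = share rescued, assumed 20% to 60%.
- q = chance, per rescued subject, of an SAE judged unrelated in the post-withdrawal window, assumed 0.5% to 3%.
- Every site is taken to apply the narrow reading.

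Expected SAEs not notified per arm = n × r × q:

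- Lowest: 60 × 0.20 × 0.005 = 0.06.
- Middle: 60 × 0.40 × 0.01 = 0.24.
- Highest: 60 × 0.60 × 0.03 = 1.08.

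Expected difference between arms = n × (difference in r) × q:

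- Equal rescue: 0.
- 40% against 20%, q = 1%: 60 × 0.20 × 0.01 = 0.12.
- 60% against 20%, q = 3%: 60 × 0.40 × 0.03 = 0.72.

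Withdrawals for reasons other than rescue fall under the same sentence and are not counted here.

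**The case against.** The strongest reply is that the last paragraph of 9.3 does not say that only related SAEs are to be notified, and it does not cancel the first paragraph. The general window runs from the last dose, so it already includes withdrawn subjects, and the later sentence can be read as an extra prompt. This stands in part: a careful site may well report everything. But on that reading the relatedness condition does nothing, since every event it covers is already reportable. A site that gives the condition a meaning will take it as the specific rule. The protocol should not leave that choice to about 45 centers.

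A second reply is that other routes catch the event. This largely stands for the data. Protocol 9.2.1 requires the AE on the case report form with its seriousness, and the End of Study call, which is arranged at the early termination visit (Protocol 5.4.4), has no causality filter. The call is only partial cover, because it can fall before the window closes and a withdrawn subject may not take it.

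A reader might infer that the SAP's SAE tables and the safety monitoring board's data inherit an imbalance between arms. The documents do not support that. SAP 10.1.5 tabulates treatment-emergent SAEs, and the board reviews all available safety data including AEs. An event recorded as Protocol 9.2.1 requires reaches both.

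A reader might also measure the effect in days of all-causality coverage. Take rescue of 20% on active and 40% on vehicle, half on Day 8 and half on Day 15 (mean 11.5 days before withdrawal), and 58 days for everyone else. Coverage is then 0.8 × 58 + 0.2 × 11.5 = 48.7 days against 0.6 × 58 + 0.4 × 11.5 = 39.4 days, 19% less on vehicle. That figure cannot be attributed to the clause. With the condition removed, rescued subjects average (38 + 45) / 2 = 41.5 days, and coverage is 0.8 × 58 + 0.2 × 41.5 = 54.7 against 0.6 × 58 + 0.4 × 41.5 = 51.4 days. A 6% gap remains because dosing stopped earlier. The rescue rates are also invented: SAP 2.3.6 assumes hazards of treatment success, not of rescue.

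**Conclusion.** The contradiction is real, and it is confined to the wording of Protocol 9.3. Where a site applies the last paragraph as the rule for withdrawn subjects, an SAE that it judges unrelated in a withdrawn or rescued subject would not be promptly notified to Pharmacovigilance, although it must still appear on the AE case report form.

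On the assumed rates the number affected is about 0.06 to 1.1 per arm, with a difference between arms from 0 to about 0.7. These are upper-end figures in one respect, since they suppose that every site takes the narrow reading. A difference by arm is possible, but it depends on unequal rescue or withdrawal, for which the documents give no figure. The primary efficacy analysis is not affected. Severity: minor.

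**What to change.** In the last paragraph of Protocol 9.3, delete the final condition of "when such a SAE occurs within 30 days of the last dose of study drug and may reasonably be related to the study drug", that is, the words after the 30-day limit that require a reasonable relation to study drug. SAEs within 30 days of the last dose would then be notified whatever their causality, in withdrawn and rescued subjects as in all others. This agrees with the first paragraph of 9.3, with 9.2.1 and with the Visit 7 reminder in 5.4.5.

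The cost is one phrase in an amendment or a site letter, and possibly a few more SAE forms. No analysis in the SAP needs to change.

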9.4 Follow-up of Adverse Events

All AEs will be followed until clinical database lock (or stabilization/resolution if it occurs before database lock). All SAEs will undergo active follow-up until resolved or the event becomes chronic or stable. Follow up data for SAEs obtained after clinical database lock will be incorporated into the safety database.

9.5 Reporting Safety Information to the IRB

The Investigator is responsible for following all local regulations for the reporting of safety information, including the reporting of SAEs to the IRB.

The Investigator must promptly report to his or her IRB all unanticipated problems involving risks to subjects. This includes death from any cause and all serious adverse events reasonably or possibly associated with the use of study drug. It is recommended that all SAEs occurring at a site, regardless of causality, be reported to the site's IRB in accordance with the IRB requirements.

ADX-102 has been filed under an IND application with the US FDA. An SAE may require safety reports to be filed to regulatory agencies if the SAE is related to the study drug and is unexpected based upon the current Investigator's Brochure. In this case, the Investigator will receive a copy of the safety report as submitted to the regulatory agencies. The Investigator is responsible for submitting the safety report (initial and follow up) or other safety information (e.g., revised Investigator's Brochure) to the IRB in accordance with the IRB requirements and maintain a copy in their files.

